9.7.2. Primary endpoint analysis (Overall survival)

The primary endpoint is OS defined as the time from first dose of study treatment in J-Ph2 to date of death due to any cause. In the absence of confirmation of death, survival time will be censored to last date the patient is known to be alive.

OS will be summarized using Kaplan-Meier methods and displayed graphically where appropriate. The median event time and 95% CI will be estimated.

9.7.3. Secondary endpoint analysis (type and duration of subsequent therapy)

Frequency of patients who received subsequent therapy will be summarized by type of therapy (eg, endocrine-based therapy, chemotherapy) and/or by line of therapy (eg, first subsequent therapy, second subsequent therapy). Median treatment durations of subsequent therapy by line of therapy will be estimated based on the Kaplan-Meier method, and duration of all subsequent therapy will be plotted by each patient.

9.7.4. Other analysis

- Clinical response of subsequent therapy - The number and proportion of each response will be summarized by type of therapy (eg, endocrine-based therapy, chemotherapy) and/or by line of therapy (eg, first subsequent therapy, second subsequent therapy). Clinical response of all subsequent therapy will be plotted by each patient along with duration of subsequent therapy.
- Time to chemotherapy - Defined as the time from first dose of study treatment in J-Ph2 to the start of first subsequent chemotherapy or death due to any cause, whichever comes first. Time to chemotherapy will be summarized using Kaplan-Meier methods and displayed graphically where appropriate. The median event time and 95% CI will be estimated.
- Palbociclib dose modification - The number and proportion of patients with dose reduction (eg, 1 dose reduction to 100 mg, 2 dose reductions to 75 mg) and the reason for dose reduction will be summarized.
- Palbociclib and letrozole treatment duration - Duration of palbociclib plus letrozole treatment will be plotted by each patient. For palbociclib, duration of treatment may be plotted by dose of palbociclib (eg, 125 mg, 100 mg, and 75 mg).

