9.4.2. Data collection time point and Data collection period

In this study, data will be collected with paper-based CRFs. The Investigator will complete CRFs for all the patients who remain in follow-up and submit them to the sponsor at the below time points;

1. Study initiation at each study site
2. Annual reporting period set by the sponsor (eg, every April)

For each patient, data collection will be continued until death unless patients withdraw consent or if the study gets sufficient OS events.

For the study, data collection will be continued until sufficient number of OS events are obtained to determine median OS.

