4.3 Other Endpoints

Clinical efficacy of subsequent treatment (categories: complete response, partial response, stable disease, progression, unknown)

- Percentage of subjects applicable to each category of clinical efficacy by each type of subsequent treatment
- Percentage of subjects applicable to each category of clinical efficacy by each treatment line

Time to start of chemotherapy

Defined as time from the date of the first dose of the investigational product in J-Ph2 to the date of the first subsequent chemotherapy or any-cause death, whichever occurred first. Surviving subjects who had not started subsequent chemotherapy will be censored at the last date of confirmed survival.

Dose Adjustment of Palbociclib

- Percentage of subjects by types of dose reduction (category: no dose reduction, dose reduction by 1 level to 100 mg, dose reduction by 2 levels to 75 mg, others)
- Percentage of subjects by reasons for dose reduction (category: adverse event, others) among those who reduced doses

Duration of Treatment with Palbociclib + Letrozole

The duration of treatment with palbociclib per dose (category: 125 mg, 100 mg, 75 mg, etc.) is defined as time from the date of the first dose to the end of treatment with the dose level.

The duration of treatment with letrozole is defined as time from the date of the first dose per investigational product in J-Ph2 to the date of the last dose of letrozole.

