6.1.2 Descriptive Summary

Continuous variables will be calculated for descriptive statistics (the number of subjects, mean, standard deviation, median, minimum, and maximum), and categorical data will be calculated for the frequency and percentage (%).

Time-to-event data will be calculated for Kaplan-Meier estimates. Data will be plotted using the Kaplan-Meier methods, and as necessary the number of events and censored subjects will be tabulated. The event follow-up period will be estimated based on a reverse Kaplan-Meier method with which the Kaplan-Meier event/censoring indicator variables for the analysis of time to event data are inversely set out.

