7.3 Other Endpoints

Clinical Efficacy of Subsequent Treatment

- Compute the percentage of subjects applicable to each category of clinical efficacy by each type of subsequent treatment.
- Compute the percentage of subjects applicable to each category of clinical efficacy by each treatment line.

The clinical efficacy of each and every subsequent treatment will be plotted for each subject along with the duration of the subsequent treatment.

Time to start of chemotherapy

The data will be summarized using the Kaplan-Meier method and plotted on graphs. The median time to start of chemotherapy and its 95%CI will be estimated.

Dose Adjustment of Palbociclib

- Compute the percentage of subjects applicable to each type of dose reduction.
- Compute the percentage of subjects applicable to each reason for dose reduction.

Duration of Treatment with Palbociclib + Letrozole

The duration of treatment with palbociclib + letrozole will be plotted for each subject. For palbociclib, the duration of treatment will be plotted by dose groups.

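### The 'time to chemotherapy' endpoint is chemotherapy-free survival, and its median should not be labelled as the time at which chemotherapy started

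*Protocol*

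**What the plan says.** Protocol 9.7.4 lists *time to chemotherapy* among the other analyses. The clock runs from the first dose in J-Ph2 "to the start of first subsequent chemotherapy or death due to any cause, whichever comes first". The analysis follows: "Time to chemotherapy will be summarized using Kaplan-Meier methods and displayed graphically where appropriate", with a median and 95% CI.

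SAP 4.3 carries the same composite under the name *time to start of chemotherapy*, running "to the date of the first subsequent chemotherapy or any-cause death, whichever occurred first". Its censoring rule matches: "Surviving subjects who had not started subsequent chemotherapy will be censored at the last date of confirmed survival". A death is therefore always an event and never a censoring. SAP 7.3 then states: "The median time to start of chemotherapy and its 95%CI will be estimated". SAP 7.4 repeats the analysis by disease-free interval and by disease site.

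Three other outputs bear on the question:

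- SAP 6.1.2 says that "as necessary the number of events and censored subjects will be tabulated". It does not divide the events by type.
- Protocol 9.7.3 and SAP 4.2 and 7.2 give the number and percentage of patients by type of subsequent therapy, with chemotherapy as one category.
- Protocol 9.7.3 and 9.7.4 and SAP 7.2 and 7.3 plan per-patient plots of the duration of, and response to, subsequent therapy.

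Neither document plans a cumulative incidence of chemotherapy.

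**The concern.** The definition and the name describe different quantities. The definition gives time alive and free of chemotherapy. The name, and the wording of the result in SAP 7.3, give the time at which chemotherapy began. A woman who dies without chemotherapy enters the statistic as an event on her date of death. A reader who sees only the reported median would take it as the time by which half the patients had started chemotherapy.

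The consequence is one of interpretation. The study is descriptive and its results are intended for publication (Protocol 9.7 and 12), so the named median is itself the result that readers carry away. The subgroup curves in SAP 7.4 have the same ambiguity: a difference by disease site could reflect mortality without chemotherapy, earlier chemotherapy, or both.

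**Working it through.** The documents state no median, event count or event split for this endpoint, so there is no planned figure to reproduce.

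**Inputs from the documents.** Treated patients: 42. Deaths by J-Ph2 completion: 8. Both are in Protocol 9.1 and SAP 3. The number of those 8 who died without chemotherapy is not given.

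**Assumption.** Let *q* be the share of first events that are deaths without chemotherapy. The documents do not give it. The range shown is 0 to 30%.

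**Step 1: direction.** At any time *t*,

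composite event probability = cumulative incidence of chemotherapy + cumulative incidence of death without chemotherapy.

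The composite is never below the chemotherapy incidence. It lies above it as soon as one patient dies chemotherapy-free. This needs no assumption about hazards.

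**Step 2: what the documents bound.** At J-Ph2 completion, 8/42 = 19.0% had died. The crude gap between patients with a composite event and patients who had started chemotherapy was therefore between 0/42 = 0 points (all 8 had chemotherapy first) and 8/42 = 19.0 points (none did).

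**Step 3: chemotherapy incidence at the reported median.** With proportional cause-specific hazards, chemotherapy incidence = (1 − *q*)(1 − *S*(*t*)), where *S* is the composite survival curve. At the median *S* = 0.5, so the incidence is (1 − *q*)/2.

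**Step 4: the time scale.** Chemotherapy incidence reaches 50% when *S* = 1 − 0.5/(1 − *q*). With constant hazards, that time divided by the composite median is −ln(1 − 0.5/(1 − *q*))/ln 2.

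| Assumed *q* | Started chemotherapy at reported median | Time to 50% chemotherapy incidence ÷ reported median |
|---|---|---|
| 0% | 50% | 1.00 |
| 5% | 47.5% | 1.08 |
| 10% | 45% | 1.17 |
| 20% | 40% | 1.42 |
| 30% | 35% | 1.81 |

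Example for *q* = 20%: 1 − 0.5/0.8 = 0.375, and −ln(0.375)/ln 2 = 1.42.

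The middle column needs proportional hazards only. The last column also needs constant hazards; if the hazards rise with time, its ratios are smaller.

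**Step 5: would censoring deaths be a better repair?** No. Under constant hazards, the median of a Kaplan-Meier curve with deaths censored is 1/(1 − *q*) times the composite median: 1.11, 1.25 and 1.43 for *q* = 10%, 20% and 30%. That is still earlier than the 1.17, 1.42 and 1.81 in the table, so chemotherapy incidence would still be overstated.

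**The case against.** The strongest reply is that nothing is hidden. Both documents state the composite in the same terms, the censoring rule fits it, and the plan avoids the common error of censoring deaths. All of that stands. A reader might infer that the Kaplan-Meier analysis is wrong, but it is not: it is valid for the quantity defined.

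A reader might also infer that the plan overstates how often chemotherapy was used. The documents do not support that. A median makes no statement about frequency, and use is reported separately by therapy type. The overstatement arises only if one minus the Kaplan-Meier curve is read as chemotherapy use.

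Nor is it right that the plan gives no information on the components. With 42 patients, the per-patient plots show a good deal about when each therapy was given. They provide no estimate or interval, however, and the percentages by type have no time scale.

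Two arguments for a large *q* are tempting. One is that "data collection will be continued until sufficient number of OS events are obtained to determine median OS" (Protocol 9.4.2), so deaths must be numerous. But a death after chemotherapy is not a first event here, so the number of deaths does not fix *q*. The other is that J-Ph2 enrolled women for whom chemotherapy was not indicated (Protocol Appendix 2). That describes entry to first-line treatment and not later lines; Protocol 7 counts chemotherapy among the standard subsequent therapies.

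Finally, precision is poor in any case. For 40% of 42 patients, ignoring censoring, the 95% half-width is about 1.96 × √(0.4 × 0.6/42) = 15 points, so gaps of 5 to 15 points lie within it. That limits the importance of the point. It does not justify a name that shifts the result in a known direction.

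**Conclusion.** The point holds as one of labelling and of a missing display. The composite and its median are sound as chemotherapy-free survival. Called the time to start of chemotherapy, the median is too early whenever a chemotherapy-free death falls at or before it, and no planned output would show by how much.

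The size cannot be derived from the documents. It is zero if every death followed chemotherapy. For an assumed 10% to 30% of first events being chemotherapy-free deaths, 45% to 35% of patients would have started chemotherapy at the reported median under proportional hazards. The direction assumes that chemotherapy starts are recorded and dated. A start that is missed in the records would push the composite event later, which is a separate problem.

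Severity is minor: the endpoint is neither primary nor secondary, and no hypothesis test depends on it.

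**What to change.** In Protocol 9.7.4 and SAP 4.3, 7.3 and 7.4:

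1. Keep the composite and its Kaplan-Meier analysis, but label it *chemotherapy-free survival* in the text, tables and figures.
2. Tabulate first events as chemotherapy, death without chemotherapy, or censored. Make this a fixed output, not one produced only when judged necessary.
3. Add the cumulative incidence of first subsequent chemotherapy by the Aalen-Johansen estimator, with death without chemotherapy as the competing event and 95% CIs. Use this curve for any statement about when chemotherapy was started.

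The cost is some wording, one small table and one curve. Therapy start dates and death dates are already on the CRFs (Protocol 9.4.1, Table 2). The only loss is that the composite median can no longer be quoted as the time to chemotherapy. Items 1 and 2 alone would resolve most of the ambiguity.

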9.7.5. Interim analysis

An interim analysis will be performed based on the data at the second data collection (i.e. based on the data collected at the first annual reporting period. [9.4.2](#)). Detailed methodology will be documented in the SAP.

9.8. Quality control

The sponsor will train investigators and study site staff with an onsite training visit or web-training on the protocol, CRFs, and any applicable study processes. Any new information relevant to the performance of this study will be forwarded to the investigator and study site staff during the study. Remote data monitoring will be conducted during the life of the study to ensure timely reporting of data, data integrity, and consistency. CRFs for all included patients will be made available to the remote data monitor for review. The study sites will be queried and managed to request resolution to any issues that may arise during the course of the study.

Onsite Monitoring visits are not planned in this study.

9.9. Limitations of the research methods

Limitations of the research method in this study include;

1. Single-arm design. Since no control group is set in the study, there is a limitation on interpretation on results, especially time-to-event endpoints.
2. Observational, retrospective design. Since this study collects data basically from medical charts of each patient, there is a potential for missing, inaccurate, or incomplete data. If the patients had been transferred to another hospital or had already passed away, data in these patients may not be fully collected or be missing information in this study. In addition, considering the observational nature, there is methodological challenges in attributing causality to outcomes.
3. Small sample size. It may be difficult to draw definitive conclusion due to lack of power.

9.10. Other aspects

9.10.1. Secondary use of data

Data obtained in this study may be used for scientific research and to promote public health. Even in such case, the personal information of patients will be protected in accordance with the applicable personal information protection law so that study patients cannot be identified.

10. PROTECTION OF HUMAN SUBJECTS

10.1. Patient information

All parties will comply with all applicable laws, including laws regarding the implementation of organizational and technical measures to ensure protection of patient personal data. Such measures will include omitting patient names or other directly identifiable data in any reports, publications, or other disclosures, except where required by applicable laws.

The personal data will be stored at the study site in encrypted electronic and/or paper form and will be password protected or secured in a locked room to ensure that only authorized study staff have access. The study site will implement appropriate technical and organizational measures to ensure that the personal data can be recovered in the event of disaster. In the event of a potential personal data breach, the study site shall be responsible for determining whether a personal data breach has in fact occurred and, if so, providing breach notifications as required by law.

To protect the rights and freedoms of natural persons with regard to the processing of personal data, when study data are compiled for transfer to Pfizer and other authorized parties, patient names will be removed and will be replaced by a single, specific, numerical code, based on a numbering system defined by Pfizer. All other identifiable data transferred to Pfizer or other authorized parties will be identified by this single, patient-specific code.

The investigator site will maintain a confidential list of patients who participated in the study, linking each patient's numerical code to his or her actual identity. In case of data transfer, Pfizer will maintain high standards of confidentiality and protection of patients' personal data consistent with the clinical study agreement and applicable privacy laws.

10.2. Patient consent

For patients who are alive and still visit the study site

The investigator must ensure that each study patient is fully informed about the nature and objectives of the study and possible risks associated with participation. Also, the investigator should appropriately and promptly respond to consultations from each patient and persons concerned. The investigator, or a person designated by the investigator, will obtain written informed consent from each patient before any data is collected. The investigator will retain the original of each patient's signed consent form.

The informed consent form must be in compliance with local regulatory requirements and legal requirements. The informed consent form used in this study, and any changes made during the course of the study, must be prospectively approved by both the IRB/ IEC and Pfizer before use.

For patients who are alive and had been transferred to another hospital

In accordance with Chapter 5 “Informed Consent” of the Ethical Guidelines for Medical and Health Research Involving Human Subjects, it is not always necessary to obtain written informed consent from the patients who had been transferred to another hospital. However, the investigator, or a person designated by the investigator, will obtain at least oral informed consent from each patient before any data is collected, and document method and content of the explanation as well as details of consent obtained.

For patients who had already passed away

In accordance with Chapter 5 “Informed Consent” of the Ethical Guidelines for Medical and Health Research Involving Human Subjects, the conduct of this study will be disclosed, and the patients' legally acceptable representatives will be guaranteed an opportunity to refuse data collection for the patients.

10.3. Patient withdrawal

Only for patients who are alive

Patients may withdraw from the study at any time at their own request. In any circumstance, every effort should be made to document patient outcome, if possible.

If the patient withdraws from the study, and also withdraws consent for disclosure of future information, no further evaluations should be performed, and no additional data should be

collected. The sponsor may retain and continue to use any data collected before such withdrawal of consent.

10.4. Institutional review board (IRB)/Independent ethics committee (IEC)

There must be prospective approval of the study protocol, protocol amendments, and other relevant documents (eg, informed consent forms if applicable) from the relevant IRBs/IECs. All correspondence with the IRB/IEC must be retained. Copies of IRB/IEC approvals must be forwarded to Pfizer.

10.5. Ethical conduct of the study

The study will be conducted in accordance with legal and regulatory requirements, as well as with scientific purpose, value and rigor and follow generally accepted research practices described in Ethical Guidelines for Medical and Health Research Involving Human Subjects issued by the Minister of Health, Labour and Welfare (MHLW).

10.6. Predictable risks and benefits for subjects

In this study, personal information will be handled in order to retrospectively collect necessary information from the medical records of individual patients. Handling of personal information complies with the ethical guidelines of the research and pays utmost attention, but there may be risk of the accidental disclosure of personal information.

This is a retrospective study, and participation in this study does not provide direct benefits. However, information obtained from participation in this research may help other patients in the future.

10.7. Report to the chief executive of the study site

Each study site's investigator shall report following to the chief executive of the study site in writing:

- 1) protocol and protocol amendments
- 2) progression of the study
- 3) discontinuation and interruption of the study.

10.8. Source of research funding and Conflict of interest

This study will be conducted with Pfizer funding. Any potential conflicts of interest in the planning, conduct, and publication of this study will be disclosed. Conflict of interest refers to an interest that may affect study results, including financial and personal relationships.

11. MANAGEMENT AND REPORTING OF ADVERSE EVENTS/ADVERSE REACTIONS

This study protocol requires human review of patient-level unstructured data; unstructured data refer to verbatim medical data, including text-based descriptions and visual depictions of

medical information, such as medical records, images of physician notes, neurological scans, X-rays, or narrative fields in a database. The reviewer is obligated to report adverse events (AEs) with explicit attribution to any Pfizer drug that appear in the reviewed information (defined per the patient population and study period specified in the protocol). Explicit attribution is not inferred by a temporal relationship between drug administration and an AE, but must be based on a definite statement of causality by a healthcare provider linking drug administration to the AE.

The requirements for reporting safety events on the non-interventional study (NIS) adverse event monitoring (AEM) Report Form to Pfizer Safety are as follows:

- All serious and non-serious AEs with explicit attribution to **any Pfizer drug** that appear in the reviewed information must be recorded on the data collection tool (e.g., chart abstraction form) and reported, within 24 hours of awareness, to Pfizer Safety using the NIS AEM Report Form.
- Scenarios involving drug exposure, including exposure during pregnancy, exposure during breast feeding, medication error, overdose, misuse, extravasation, lack of efficacy, and occupational exposure associated with the use of a Pfizer product must be reported, within 24 hours of awareness, to Pfizer Safety using the NIS AEM Report Form.

For these AEs with an explicit attribution or scenarios involving exposure to a Pfizer product, the safety information identified in the unstructured data reviewed is captured in the Event Narrative section of the report form, and constitutes all clinical information known regarding these AEs. No follow-up on related AEs will be conducted.

All the demographic fields on the NIS AEM Report Form may not necessarily be completed, as the form designates, since not all elements will be available due to privacy concerns with the use of secondary data sources. While not all demographic fields will be completed, at the very least, at least one patient identifier (eg, gender, age as captured in the narrative field of the form) will be reported on the NIS AEM Report Form, thus allowing the report to be considered a valid one in accordance with pharmacovigilance legislation. All identifiers will be limited to generalities, such as the statement “A 35-year-old female...” or “An elderly male...” Other identifiers will have been removed.

Additionally, the onset/start dates and stop dates for “Illness”, “Study Drug”, and “Drug Name” may be documented in month/year (mmm/yyyy) format rather than identifying the actual date of occurrence within the month /year of occurrence in the day/month/year (DD/MMM/YYYY) format.

All research staff members must complete the following Pfizer training requirements:

- “*YRR Training for Vendors*”.

These trainings must be completed by research staff members prior to the start of data collection. All trainings include a “Confirmation of Training Certificate” (for signature by the trainee) as a record of completion of the training, which must be kept in a retrievable format. Copies of all signed training certificates must be provided to Pfizer.

Re-training must be completed on an annual basis using the most current Your Reporting Responsibilities training materials.

